### 6.2.2 Clinical Laboratory Assessments

Individual data listings of laboratory results will be presented for each subject. The observed values and change from baseline of all hematology, clinical chemistry, coagulation and urinalysis results (observed values) will be summarized according to section 6.1.1. Laboratory assessments that are outside of normal ranges and with potential clinical importance will be summarized and flagged in the listings with the PI's or investigator's assessment such as NCS or CS. Shift tables of hematology, clinical chemistry, coagulation and urinalysis results will be generated to summarize the normal, NCS and CS status changes from baseline.

### 6.2.3 Vital Signs

Observed and change from baseline - vital sign values (body weight, BMI, blood pressure [BP], pulse, respiratory rate, and tympanic temperature) at each day and time-point will be listed and summarized.

### 6.2.4 12-lead Electrocardiograms

Average and individual triplicate ECG intervals will be listed with mean change from baseline by subject, day, and time point. Observed and change from baseline values of ECG parameters will be

summarized. The worst case of triplicated status of 12-lead ECG parameters, Normal, Abnormal NCS, and Abnormal CS, and their shifts from baseline will be summarized.

#### **6.2.5 Physical Examination**

The clinical findings (Abnormal NCS and Abnormal CS) on PE and severity will be listed.

#### **6.2.6 Injection Site Reactions**

Multiple syringes may be injected subcutaneously in the right upper abdomen (if not applicable, left upper abdomen) as the dose increases. All injection site irritation events will be documented as AEs and included in the AEs analysis in the Section 6.2.1. The number and percentage of subjects with specific site reactions such as erythema and edema will be summarized by treatment group, day, time point, and Draize scale. In addition, diameter of affected areas will be summarized descriptively by treatment group, day and time point.

#### **6.2.7 Immunogenicity**

Immunogenicity assessments will be performed when deemed necessary by the Principal Investigator or the Sponsor in any of the following cases:

- When ADA formation is suspected based on PK/PD analysis results
- When biomarker changes related to drug efficacy are not observed at expected pharmacologically effective doses
- When AEs suspected as immune responses occur after administration
- When necessary for other clinical/scientific reasons

Anti-drug antibodies (ADAbs, anti-HM15912 antibodies) will be summarized categorically, hierarchically displaying the Positive and Negative results from screening assay and confirmatory assay by treatment group and visit. Confirmed positive ADAbs will be further summarized by titer fold categories. Domain specificity will be listed along with the screening, confirmatory assay and titer results.

Neutralizing antibodies (Nabs) will be summarized categorically, hierarchically displaying the Positive and Negative results from screening and confirmatory assay by treatment group and visit. Cross reactivity for confirmed positive Nabs will be summarized by treatment group and visit.

Anti-polyethylene glycol antibodies (anti-PEG) will be summarized categorically, displaying the Positive and Negative results from screening assay and specificity by treatment group and visit. The titer results are listed only.

### 6.3 Pharmacokinetic Analyses

#### 6.3.1 PK Concentration

Concentration of HM15912 will be summarized descriptively by treatment group and time point. A line plot for mean concentration +/- standard deviation over time will be generated for the PK set with dose level overlaid. Line plots on linear and log scales of HM15912 individual subject concentration overlaid with the mean concentration for each cohort will be plotted separately.

#### 6.3.2 PK Parameter

The following PK parameters will be summarized by treatment group for the PK Analysis Set.

- Maximum concentration ( $C_{max}$ ) is defined as the maximum HM15912 concentration measured after single SC dose
- Time to reach  $C_{max}$  ( $T_{max}$ ) is defined as the time from initial injection to time of  $C_{max}$
- Area under the concentration-time curve for HM15912 up to the last point with concentrations above the lower limit of quantification (LLOQ),  $AUC_{0-last}$ , will be calculated by linear-up log-down method.
- Area under the concentration-time curve with extrapolation to infinity for HM15912,  $AUC_{0-inf}$ , will be calculated by  $AUC_{0-last} + C_{last}/\lambda_z$ , where  $C_{last}$  is the last observed concentration ( $_obs$ ), or the last predicted concentration ( $_pred$ ).
- $AUC\%_{extrap}$ : Percentage of  $AUC_{inf}$  that is due to extrapolation beyond  $t_{last}$
- $\lambda_z$ , first-order terminal elimination rate constant, calculated by linear regression of time vs. log concentration curve in the terminal phase. For  $\lambda_z$  to be acceptable, it shall be determined over a time interval equal to at least  $1.5 \times t_{1/2}/\lambda_z$ , with at least 3 different time points in the terminal phase for the regression analysis, and the coefficient of determination  $Adj\_RSq$  shall be  $\geq 0.8$ . If at least one of these three conditions is not fulfilled, the parameters depending on  $\lambda_z$  (e.g.,  $AUC_{0-inf}$ , the terminal half-life  $t_{1/2}$ ,  $\lambda_z$ , CL and  $V_z$ ) shall be flagged as not reliable if calculated and listed. They will generally be excluded from descriptive statistics and statistical testing procedures, unless otherwise judged by the pharmacometrist in charge of PK analysis.
- Apparent terminal half-life  $t_{1/2}$ , will be determined from equation  $\ln 2/\lambda_z$ .
- CL ( $_obs$ ,  $_pred$ ), apparent total body clearance will be calculated by  $Dose/AUC_{0-inf}$ . Note, the Dose in calculating CL for HM15912 will be the total administered dose, which is the subcutaneous dose.
- $V_z$  ( $_obs$ ,  $_pred$ ), apparent volume of distribution at terminal phase and will be calculated by  $CL/\lambda_z$ .
- Apparent clearance divided by bioavailability (CL/F)
- Apparent volume of distribution at terminal phase divided by bioavailability (Vz/F)

Box plots of  $C_{max}$ ,  $AUC_{0-last}$  and  $AUC_{0-inf}$  for each cohort may be generated. The planned last sampling

time of each cohort will be informed as an annotation at  $AUC_{0-\text{last}}$  of summary stat and box plot as planned last sampling times for Cohort 1-3 and Cohort 4-5 are different as Day 30 and Day 44, respectively.

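### The span condition for accepting λz in SAP 6.3.2 is printed as a time squared, so it cannot be applied as written and its result changes with the time unit

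*SAP*

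**What the plan says.** SAP 6.3.2 describes λz as the "first-order terminal elimination rate constant, calculated by linear regression of time vs. log concentration curve in the terminal phase". It then sets three acceptance conditions:

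- On the regression interval, "it shall be determined over a time interval equal to at least" "1.5 \times t_{1/2}/\lambda_z" (as machine-read), that is, 1.5 × t1/2/λz.
- The fit must be made "with at least 3 different time points in the terminal phase for the regression analysis".
- The adjusted R² must be at least 0.8.

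The next bullet says that t1/2 "will be determined from equation" ln2/λz.

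On failure the section reads "If at least one of these three conditions is not fulfilled, the parameters depending on" λz are flagged as not reliable; the examples named are AUC0-inf, t1/2, λz, CL and Vz. It continues: "They will generally be excluded from descriptive statistics and statistical testing procedures, unless otherwise judged by the pharmacometrist in charge of PK analysis".

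The same section notes that the "planned last sampling times for Cohort 1-3 and Cohort 4-5 are different as Day 30 and Day 44, respectively". Protocol 3.2.2 asks only for at least three terminal points and has no span rule, so the SAP is the only source for this condition.

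**The concern.** A span condition should compare a length of time with a multiple of the half-life. Here the half-life is divided by a rate constant. A time divided by a reciprocal time is a time squared, so the comparison has no meaning until someone chooses a clock unit, and the answer then depends on that choice.

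This is an operative rule. One failed condition is enough to flag the λz-dependent parameters and, by default, remove them. Those parameters are most of the secondary PK endpoints in SAP 3.2. AUC0-inf is also one of the three parameters in the power model of SAP 6.3.3. It carries extra weight there because AUC0-last is planned to end on Day 30 at the three lower doses and on Day 44 at the two higher ones.

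**Working it through.** The plan states no half-life limit, so there is no figure of its own to reproduce. The check is of units first, then of what the printed rule would imply.

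**Inputs**

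- Printed condition: span ≥ 1.5 × t1/2/λz (SAP 6.3.2).
- t1/2 = ln2/λz, so λz = ln2/t1/2 (SAP 6.3.2).
- Last planned PK sample: Day 30 in Cohorts 1–3 and Day 44 in Cohorts 4–5 (SAP 6.3.2). The nominal times are 696 h and 1032 h, each ±72 h (Protocol Tables 3-1 and 3-2, the PD schedule).
- Day 7 is 144 h in the same tables.
- Assumptions: the PK sampling table is redacted, so the start of the terminal phase is taken as anywhere from time 0 to Day 7. The time unit is not stated, so both hours and days are tried.

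**Units**

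Substituting λz gives span ≥ 1.5 × t1/2²/ln2. The left side is a time and the right side is a time squared.

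**Longest half-life that passes**

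- As printed: t1/2 ≤ √(span × ln2/1.5).
- With a bound of 1.5 × t1/2: t1/2 ≤ span/1.5.

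| Fit interval | Span | Printed rule, hours | Printed rule, days | 1.5 × t1/2 |
|---|---|---|---|---|
| Cohorts 1–3, from Day 7 | 552 h (23 d) | 16.0 h | 3.26 d = 78.2 h | 368 h |
| Cohorts 1–3, from time 0 | 696 h (29 d) | 17.9 h | 3.66 d = 87.9 h | 464 h |
| Cohorts 4–5, from Day 7 | 888 h (37 d) | 20.3 h | 4.13 d = 99.2 h | 592 h |
| Cohorts 4–5, from time 0 | 1032 h (43 d) | 21.8 h | 4.46 d = 107.0 h | 688 h |

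First row, written out: √(552 × 0.693/1.5) = √255 = 16.0 h, and √(23 × 0.693/1.5) = √10.6 = 3.26 d. Changing from hours to days moves the limit by √24 = 4.9. The last column does not depend on the unit.

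The ±72 h visit windows widen the ranges only slightly. They become 14.9 h (span 480 h) to 22.6 h (span 1104 h) with time in hours, and 73.0 h to 110.7 h with time in days.

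**One subject, two answers**

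Take t1/2 = 72 h (3 d), Cohorts 1–3, fitted from Day 7 to Day 30:

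- In days: 1.5 × 3²/0.693 = 19.5, against a span of 23. Passes.
- In hours: 1.5 × 72²/0.693 = 11,218, against a span of 552. Fails.
- With 1.5 × t1/2: 108 h needed, against 552 h. Passes in either unit.

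**The case against.** The strongest reply is that this is a typographical matter. The text was read from PDF, and the slash may stand for a subscript label, meaning the half-life associated with λz. Two things support that. The same bullet lists λz among the parameters that depend on λz, which makes sense only if λz there is a label on t1/2. And the condition speaks of a time interval, so a bound of 1.5 × t1/2 can be recovered by a careful reader. This largely stands: 1.5 × t1/2 is the likely intent, and an analysis program would probably apply it. It does not remove the need to state the rule correctly, because the readable text does not settle what was meant.

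It is also fair to say that the consequences are contained. Flagged values are still listed, and the pharmacometrist may override the exclusion. SAP 4 and 6.1.4 require exclusions to be documented. Cmax, Tmax and AUC0-last do not depend on λz, so two of the three dose-proportionality models are unaffected. All of that stands. It limits the damage but leaves the printed threshold wrong.

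Two stronger readings are tempting, and the documents support neither:

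- *A reader might infer that every subject with a half-life above 16–22 h will lose these endpoints.* That limit exists only if time is in hours, which the SAP does not say, and exclusion is a default that can be overridden. Protocol 1.1 describes a molecule built for a longer half-life but shows no figure for it.
- *A reader might infer that the conditions let a mostly extrapolated AUC0-inf through, because they set no limit on AUC%extrap.* With a well-fitted line over at least 1.5 half-lives ending at the last quantifiable sample, the extrapolated part is at most 2^(−1.5) = 35% of the area from the start of the fit onward, and a smaller share of the whole. AUC%extrap is also a declared secondary endpoint that will be summarized, so readers will see it. A fixed percentage cut-off would be a preference with no source in the documents.

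**Conclusion.** The point holds as an error in an operative rule. As printed, the bound is 1.5 × t1/2²/ln2, a time squared, and the rule cannot be applied without an unstated choice of unit. The implied half-life limit is about 16–22 h with time in hours and about 78–107 h with time in days, for a terminal phase starting between time 0 and Day 7 and nominal last samples at 696 h and 1032 h. With the likely intended bound the limits are 368–688 h.

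The unit error follows from the SAP's own definitions and needs no assumption about the drug. How many subjects would be affected cannot be derived, because the half-life of HM15912, the PK sampling times and the time unit are not shown. If the source file has a subscript in place of the slash, the point reduces to a clarification. On the text as it reads, it should be corrected, since the default inclusion of AUC0-inf, t1/2, λz, CL and Vz depends on it.

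**What to change.** In SAP 6.3.2, replace the span condition with: *over a time interval of at least 1.5 × t1/2, where t1/2 = ln2/λz from the same regression*. Leave the three-point and adjusted R² conditions as they are.

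The cost is one phrase and a check that the analysis program applies the same bound. If it already uses 1.5 × t1/2, no result changes. The correction belongs before database lock and unblinding, when SAP 1 says the plan is final. If that time has passed, the clinical study report should state which bound was used, in line with Protocol 8 on describing deviations. The change does not remove the pharmacometrist's override and is not meant to; it gives the override a defined rule to depart from.

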- q. Blood will be collected for GIP, GLP-1, C-peptide, glucagon and insulin immediately before administration and once daily on Days 4 and 7, at the Day 17 Outpatient visit and at the Day 30 Outpatient visit. If the PK sampling time points are changed, sampling times may be adjusted accordingly.
- r. Blood will be collected for IGF-1 and KGF immediately before administration and once daily on Days 4 and 7, at the Day 17 Outpatient visit and at the Day 30 Outpatient visit. If the PK sampling time points are changed, sampling times may be adjusted accordingly.
- s. Alcohol breath test procedure could be replaced with the examination by interview to avoid infection of COVID-19.

Table 2 Citrulline Sampling Schedule for Exploring PK Samples and PD

Table 2-1 Citrulline Sampling Schedule for Exploring PK Samples and PD (Cohort 1~3)

■■■	■■■■■	■■■■■
■■■	■■■■■	■■■■■
■■■	■■■■■	■■■■■
■■■	■■■■■	■■■■■
■■■	■■■■■	■■■■■

- a. Sampling times may be adjusted between the cohorts in case available PK data show that other time points would be more beneficial.
- b. Samples will be collected with an empty stomach.
- c. PK and citrulline samples may be collected ± 1 day (24 hours) from the scheduled sampling time points at the Days 10 and 17 Outpatient visits. The samples may also be collected ± 1 day (24 hours) from the scheduled sampling time points in case there is an additional Outpatient visit.
- d. PK and citrulline samples may be collected ± 3 days (72 hours) from the scheduled sampling time points at the Day 30 Outpatient visit.

Table 2-2 Citrulline Sampling Schedule for Exploring PK Samples and PD (Cohort 4, 5)

[REDACTED]	[REDACTED]	[REDACTED]

- a. Sampling times may be adjusted between the cohorts in case available PK data show that other time points would be more beneficial.
- b. Samples will be collected with an empty stomach.
- c. PK and citrulline samples may be collected ± 1 day (24 hours) from the scheduled sampling time points at the Days 10 and 17 Outpatient visits. The samples may also be collected ± 1 day (24 hours) from the scheduled sampling time points in case there is an additional Outpatient visit.
- d. PK and citrulline samples may be collected ± 3 days (72 hours) from the scheduled sampling time points at the Day 30 and Day 44 Outpatient visit.

Table 3 PD Sampling Schedule**Table 3-1 PD Sampling Schedule (Cohort 1~3)**

Study Day	Screening -28 ~ -2	-1	1		2	3	4	5	6	7	OP 10	OP 17	FU 30

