### 6.1.4 Handling of Outliers and Unquantifiable Measurements

Prior to unblinding, PK data will be reviewed by the PK scientist and statistician to assess whether individual concentration values are inconsistent with other values from the same subject or if there are errors with the samples. Determination of data points subject to re-analysis or removal from determination of PK parameters (i.e., implausible data) will be documented prior to unblinding. PK and PD parameter results will also be reviewed by appropriate representatives and a determination of plausibility will be made. Individual subject results deemed implausible may be removed prior to summarization of PK and PD parameter results by treatment group. Removal of individual subject PK/PD parameter results will be documented.

The following rules will be applied when blood samples are assayed as below the limit of quantitation (BLQ) or if individual concentration results are deemed implausible prior to database lock:

[REDACTED]

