### 6.3.3 Dose Proportionality

The power model will be used to analyze the dose proportionality in  $AUC_{0-\text{last}}$ ,  $AUC_{0-\text{inf}}$  and  $C_{\text{max}}$  of HM15912. The estimate of  $\beta$  and the corresponding 90% CI will be derived.

The power model is defined as follows:

$$\log(PK_i) = \alpha + (\beta) * \log(\text{dose}_i) + \varepsilon_i$$

where  $PK_i$  is the PK parameter ( $AUC$  or  $C_{\text{max}}$ ) observation for the subject  $i$ .

$\alpha$  is the population intercept.

$\beta$  is the population slope.

$\text{dose}_i$  is the dosage(mg) for the subject  $i$ .

$\varepsilon_i$  is the random error;  $\varepsilon_i \sim N(0, \sigma^2_{\varepsilon})$  and independent.

The assumption for the Power Model is that the underlying relationship between log(PK parameter) and log(dose) is linear. The dose proportionality corresponds to the ratio of dose normalized geometric means ( $R_{\text{dnm}}$ ), which is defined as ratio of the predicted geometric mean of the highest dose relative to the predicted geometric mean of the lowest dose. The dose proportionality would be declared when the 90% CI for the  $R_{\text{dnm}}$  falls entirely within the limit of 0.8 to 1.25. Scatter plot of log(PK parameter) and log(dose) will be plotted with an estimated line.

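### AUC0-last enters the dose-proportionality model although planned PK sampling ends on Day 30 at the three lowest doses and Day 44 at the two highest; a partial AUC to a common time should be added

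*SAP*

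**What the plan says.** - SAP 6.3.2 runs AUC0-last to the last concentration above the LLOQ, by the linear-up log-down method. It states that "planned last sampling times for Cohort 1-3 and Cohort 4-5 are different as Day 30 and Day 44, respectively" and has this annotated on the AUC0-last summary statistics and box plot.
- Protocol Table 2-2, footnote d, confirms the late PK sample in Cohorts 4-5: a window of 3 days either side is allowed "from the scheduled sampling time points at the Day 30 and Day 44 Outpatient visit". The PK times are blacked out. Protocol Tables 3-1 and 3-2 give the same days as 696 h and 1032 h.
- SAP 6.3.3: "The power model will be used to analyze the dose proportionality in" AUC0-last, AUC0-inf and Cmax. The dose term "is the dosage(mg) for the subject". Proportionality is declared when the 90% CI for Rdnm "falls entirely within the limit of 0.8 to 1.25". The section mentions neither the unequal sampling nor what follows if the three parameters disagree.
- SAP 6.3.2 accepts lambda_z only under conditions. One is that "it shall be determined over a time interval equal to at least" 1.5 half-lives; the others are at least 3 points and an adjusted R-squared of 0.8 or more. On parameters that fail: "They will generally be excluded from descriptive statistics and statistical testing procedures", subject to the pharmacometrist's judgement.

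**The concern.** The step in planned sampling coincides with the split between low doses (0.05, 0.1, 0.5 mg/kg) and high doses (1.0, 1.5 mg/kg). If drug is still quantifiable at Day 30 in every cohort, AUC0-last at the high doses includes up to 14 more days of exposure than at the low doses. The regression reads that as more-than-proportional exposure. More subjects would not remove it. For a truly proportional drug it makes the rule harder to meet, and it can mask a true slope below 1. The annotation in SAP 6.3.2 warns a reader of the summary but does not change the slope or the declaration in SAP 6.3.3.

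**Working it through.** The plan gives no bias or power figure for this analysis, so there is none to reproduce.

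**Inputs.** Doses 0.05, 0.1, 0.5, 1.0 and 1.5 mg/kg with 6 active subjects each (SAP Table 1). Nominal ends: (30-1) x 24 = 696 h and (44-1) x 24 = 1032 h, that is 29 d and 43 d after dosing. Human half-life and CV are not in the readable text and are assumed below.

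**Weight of the step.** Centred ln(dose): -1.879, -1.185, 0.424, 1.117, 1.523. Sum of squares 8.680 (52.08 with 6 per dose). Slope of a Cohort 4-5 indicator on ln(dose): w = (1.117 + 1.523)/8.680 = 0.304.

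**Shift against a common Day 30 end**, with Cohorts 1-3 quantifiable at Day 30 and Cohorts 4-5 to Day 44: shift = w x ln[AUC(0-1032 h)/AUC(0-696 h)]. The range is 1.5/0.05 = 30-fold, so Rdnm is multiplied by 30^shift. For mono-exponential decline AUC(0-T) is proportional to f(T) = 1 - 2^(-T/half-life).

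| Assumed half-life | f(29 d) | f(43 d) | Ratio | Slope shift | Rdnm factor |
|---|---|---|---|---|---|
| 3 d | 0.999 | 1.000 | 1.001 | 0.000 | 1.00 |
| 5 d | 0.982 | 0.997 | 1.016 | 0.005 | 1.02 |
| 7 d | 0.943 | 0.986 | 1.045 | 0.013 | 1.05 |
| 10 d | 0.866 | 0.949 | 1.096 | 0.028 | 1.10 |
| 14 d | 0.762 | 0.881 | 1.156 | 0.044 | 1.16 |

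With an assumed SC absorption half-life of 2 d the factors are 1.00, 1.03, 1.07, 1.13 and 1.20.

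**Limit.** Flat concentrations to Day 44: 0.304 x ln(1032/696) = 0.304 x 0.394 = 0.120, factor 30^0.120 = 1.50. This is a ceiling at nominal times if mean concentration after Day 30 is not above the mean before it. For scale, the rule tolerates a slope within ln(1.25)/ln(30) = 0.066 of 1. The mono-exponential shift alone reaches that at a half-life of about 22 d.

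**If low doses fall below LLOQ first.** Assume a half-life of 5 d with Cohort 5 reaching LLOQ at 43 d. Lower doses reach it earlier by 5 x log2(1.5/dose) days: at 40.1, 35.1, 23.5 and 18.5 d for 1.0, 0.5, 0.1 and 0.05 mg/kg. Slope shift = sum of centred ln(dose) x ln f(T), divided by 8.680:

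| Schedule | AUC0-last ends, lowest to highest dose (d) | Shift |
|---|---|---|
| As planned | 18.5, 23.5, 29, 40.1, 43 | 0.0210 |
| All to Day 44 | 18.5, 23.5, 35.1, 40.1, 43 | 0.0215 |
| All to Day 30 | 18.5, 23.5, 29, 29, 29 | 0.0164 |

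Most of the shift is LLOQ truncation, and longer sampling of the low doses would not reduce it. Two other assumed cases, planned versus all to Day 44: half-life 7 d, Cohort 5 at LLOQ at 60 d, 0.0186 versus 0.0182; half-life 14 d, LLOQ at 80 d, 0.1775 versus 0.1846.

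**Effect on the declaration (illustrative).** Chance of declaring proportionality when it is true. Sigma = sqrt(ln(1 + CV^2)), t(0.95, 28 df) = 1.701, 30-fold mg/kg range, integrated over the residual variance:

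| CV | No shift | Factor 1.02 | 1.05 | 1.10 | 1.16 |
|---|---|---|---|---|---|
| 15% | 85.3% | 83.8% | 76.4% | 54.9% | 27.2% |
| 20% | 50.8% | 49.9% | 45.5% | 33.3% | 18.1% |
| 25% | 19.8% | 19.5% | 18.2% | 14.4% | 9.2% |
| 30% | 4.6% | 4.5% | 4.3% | 3.6% | 2.6% |

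The SAP model uses mg. With weights assumed uniform from 50 to 80 kg, the dose range widens to about 42-fold and the no-shift column falls to about 76%, 36%, 11% and 2%.

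**Is AUC0-inf available?** PK samples on Days 7, 10, 17 and 30 span 23 d, and 23/1.5 = 15.3 d. The interval condition for lambda_z can therefore be met for half-lives up to about 15 d if Day 30 is quantifiable.

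**The case against.** The case against runs as follows. The SAP discloses the unequal ends. AUC0-inf and Cmax go through the same model, and AUC0-inf should usually be available up to a half-life of about 15 d. The protocol names AUC0-t for this analysis and allows additional ones. At a CV of 20% or more the rule often fails with 6 subjects per dose even without a shift. A partial AUC also needs lambda_z in low-dose subjects who drop below LLOQ early.

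All of this stands, and it limits the harm. It does not leave SAP 6.3.3 complete. Disclosure does not correct the slope, AUC0-inf generally loses subjects with an unacceptable lambda_z, and nothing says which AUC result governs if they differ.

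Three stronger readings are tempting and not supported:
- A reader might infer a bias of 0.12. That requires flat concentrations to Day 44, and the readable text gives no human half-life.
- A reader might infer that all quantifiable exposure after Day 30 in Cohorts 4-5 is bias caused by the schedule, so that sampling Cohorts 1-3 to Day 44 would cure it. Where the low doses are below LLOQ before Day 30, extending their sampling changes little.
- A reader might take the power table as a forecast for this trial. CV and half-life are assumed, and the table is on the mg/kg scale.

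**Conclusion.** The point holds as a modest, cheaply corrected weakness. The AUC0-last slope is shifted upward relative to a common Day 30 end, provided Cohorts 1-3 are quantifiable at Day 30 and Cohorts 4-5 have quantifiable exposure after it. The plausible size depends on half-life: negligible at 3 d, and from 5 to 14 d between a small and a material share of the 0.066 tolerance. It matters for the declaration mainly when half-life is long and CV is low. The direction and the flat-concentration limit rest on the documents' doses and times; the rest depends on the assumed half-life, profile shape and CV. The analysis is secondary and unpowered, and no safety conclusion depends on it.

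**What to change.** Amend SAP 6.3.3 before unblinding:
- Add a partial AUC from 0 to 696 h for all cohorts and enter it in the same power model. Prespecify 384 h (Day 17) as a second partial AUC, so that no cut-off is chosen after concentrations are seen.
- Use linear-up log-down. Interpolate to the cut-off where a later quantifiable sample exists; extrapolate only with an accepted lambda_z.
- Where the last quantifiable sample is before the cut-off and lambda_z is not accepted, set the partial AUC to missing and report the count by cohort.
- Base the AUC proportionality statement on AUC0-inf and the partial AUC, and report any disagreement as inconclusive.
- Keep AUC0-last in the model as supportive, with one sentence that its planned end differs by dose group.

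SAP 6.1.4 already provides a suitable step for documenting exclusions: "Prior to unblinding, PK data will be reviewed by the PK scientist and statistician".

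Cost: SAP wording and the added NCA parameter at its two cut-offs. No new samples are needed and no protocol-named parameter is dropped; Protocol 8.8 allows additional analyses. The downside is that a partial AUC omits exposure after the cut-off, which AUC0-inf covers only where lambda_z is acceptable.
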